5.1.6. Visits 3 (Period 1) and 6 (Period 2): 24 hours post-exposure

1. Review any adverse events
2. Vital signs, resting blood pressure, oxygen saturation
3. WSP Exposure symptom questionnaire
4. Venipuncture (CBC with differential, serum cytokines, serum C-reactive peptide, lipid panel, LDH, fibrinogen, PT, aPTT, INR, gT and metabolite levels)
5. Spirometry
6. Sputum induction
7. .

At least a 4 week, but no more than an 8 week washout is required between Period 1 and Period 2.

5.1.7. Visit 7: Study completion, 5-10 days post-exposure

1. Review any adverse events
2. Vital signs, oxygen saturation, symptom questionnaire
3. If the participant has any health symptoms or concerns, they will receive a physical examination and evaluation by a study physician.

We will contact participants 1 month after participation to follow up and ask about health status.

If the participant develops an upper or lower respiratory tract illness between V0 and V1 or between periods, we will postpone the next study visit for a minimum of 4 weeks after resolution of symptoms. In this case, if V1 occurs >1 month from V0, or if V4 occurs >2 months from V3, to prioritize participant safety we will bring the subject in for an additional visit to collect safety labs, perform spirometry, and review interval history.

If the participant has an illness mid-dosing of the gamma tocopherol/placebo or fails to adhere to the dosing regimen, participants will return 4 weeks after they have taken their last dose or 4 weeks after resolution of symptoms. At that visit, gamma tocopherol/placebo will be re-dispensed. To prioritize participant safety we will review interval history. Subjects with an illness during dosing, we will additionally collect safety labs, and perform spirometry.

All subjects with a symptomatic Covid 19 infection will be deferred for 90 days. Baseline spirometry and safety labs will be assessed prior to any gamma tocopherol/placebo dosing and WSP exposure.

5.1.8. Table of study procedures

	General Screen	Screening WSP Exposure	V0 (Baseline)	V1 (Training)	V2 (period 1) V5 (period 2)	V4 (Dispense study drug)	V3 (period 1) V6 (period 2)	V7 (Completion visit)
Consent	X	X	X					
Review history/AE's	X	X	X	X	X	X	X	X
Vital Signs	X	X	X	X	X	X	X	X
Urine hCG (females only)	X	X	X	X	X	X		
Dispense study drug				X		X		
WSP Symptom Questionnaire		X			X			X
GI symptom diary				X	X	X		
Spirometry (FEV ₁)	X	X	X	X	X	X (asthmatic participants only)		X
Allergy Skin Prick Test	X							
Physical Exam		X	X					
Venipuncture		X	X		X		X	
CV measurements: FMD, LVS				X (FMD, LVS only)	X)	
Sputum Induction	X	X	X		X			X
2 hour WSP chamber exposure		X			X			

5.2. Protocols for Measurements and Observations

5.2.1 Woodsmoke particle chamber exposure

We will employ the exposure protocol described by (20). We will heat whiteoak wood on an electric heating element (Brinkmann, Dallas, Texas, USA) in a Quadrafile 3100 woodstove (Colville, Washington, USA) to generate wood smoke. The smoke will be extracted from the chimney and injected into the chamber air stream, and wood smoke particle concentration will be

controlled using a tapered element oscillating microbalance (TEOM®; Thermo Fisher Scientific, Franklin, Massachusetts, USA) to measure the chamber concentration. A DustTrak 8530 aerosol monitor (TSI, Shoreview, Minnesota, USA) will also be used as an alternative monitor for independent verification of proper TEOM® operation. The particle number concentration will be measured with a Model 3022A CPC (TSI, Shoreview, Minnesota, USA) and the number and size distribution will be measured with a Model 3080L SMPS (TSI). The particle concentration will be verified by weighing filters obtained using a versatile air pollution sampler (VAPS; URG, Chapel Hill, North Carolina, USA). The chamber temperature and humidity will be controlled to approximately 22°C and 40%, respectively. The target average concentration of WSP we will use for this study will be $500 \mu\text{g}/\text{m}^3$, with mild exercise to increase minute ventilation (20 L/min/m² BSA) for 15 minute periods, alternating with 15 minute rest periods across an overall 2 hour total exposure period.

5.2.2. Induced sputum

Sputum samples will be collected using a specific sputum induction protocol in which FEV₁ and FVC will be measured to determine the baseline FEV₁ and FVC values. Asthmatic individuals will be pretreated with 2 to 4 puffs of albuterol prior to the procedure, and post-albuterol spirometry will be collected. The FEV₁ values that match a 10% and 20% fall from baseline will be calculated. An ultrasonic nebulizer will be filled with 15 mL of 3% hypertonic saline (inhalation grade for respiratory use only) to begin the test. The nebulizer will be set to the maximum output setting and turned on. The subject will be instructed to breathe normally (i.e. tidal breaths) through the nebulizer mouthpiece for 7 minutes. The saline will be nebulized through the mouthpiece in a jet stream and inhaled. The nose will not be occluded for this procedure. Prior to expectoration, subjects will blow their nose, rinse their mouth with water, and clear their throat to avoid the inclusion of non-airway fluid samples. The subject will also be encouraged to come off the mouthpiece at any time to cough if a sputum sample from the lower airways (i.e. not from the back of the throat) is ready for expectoration. The sample will be coughed into a sterile specimen jar and capped. Following repeat measurement of FEV₁ after the first 7 minute inhalation period, the concentration of saline will be increased from 3% to 4%, provided the FEV₁ falls by <10% from the baseline value. The same procedure will be followed for the final 7 minute inhalation period using 5% hypertonic saline. The nebulization will be stopped at that point, or earlier, if a sputum sample of good quality is obtained (i.e. visible sputum plugs). The 4% and 5% saline solutions will be mixed for each induction by study staff just prior to induction and a volume of 15-20 mL will be used on each occasion.

5.2.3. Spirometry

Spirometry will be performed according to American Thoracic Society guidelines. Subjects will inhale as deeply as possible, then exhale as rapidly and completely as possible into the spirometer. Measurements obtained from each maneuver include the FVC, the FEV₁, the maximal mid-expiratory flow rate (FEF 25-75%) and the peak flow (PF). The largest FVC and FEV₁, from at least 3 acceptable trials will be selected for analysis and subject must meet the appropriate inclusion/exclusion criteria based on comparison of the subject's measurements to the predicted value for an individual of his/her gender, age, race and height with NHANES III as the predicted set.

5.2.4. Flow mediated dilation measured by brachial artery ultrasound:

Vascular endothelial function will be assessed by measuring flow-mediated dilation of the brachial artery. Ultrasound images of the right brachial artery proximal to the antecubital fossa will be acquired using a Philips EPIQ 7 ultrasound machine equipped with a high-frequency (L9-3) broadband linear-array transducer. The baseline images will be obtained after 10 minutes of supine rest. Flow-mediated (endothelium-dependent) dilation will be assessed by determining the change in arterial diameter in response to reactive hyperemia. Reactive hyperemia will be induced by inflating a pneumatic occlusion cuff placed around the upper forearm to a suprasystolic pressure (approximately 200 mmHg) for five minutes. Images of the artery will be recorded for two minutes after cuff deflation. Gated end-diastolic images will be stored in a digital format on a personal computer for subsequent offline quantification. Measurements will be performed using customized software (Brachial Tools, Medical Imaging Applications, LLC). Arterial diameter will be measured from the lumen-intimal interfaces of the proximal and distal arterial walls. Data from at least ten end-diastolic frames will be averaged for the baseline measurement and from at least three frames at maximum dilation during reactive hyperemia FMD will be calculated as the percent change in diameter from baseline.

5.2.5. Left ventricular strain

LV strain will be assessed by measuring global longitudinal strain using 2-dimensional speckle tracking echocardiography. Speckle tracking imaging is a relatively new technique with which myocardial mechanics can be quantified by tracking groups of intramyocardial speckles. Global longitudinal strain, the average fractional change in myocardial segment length, is a more sensitive index of LV contractility than ejection fraction or other standard measures. Apical 4-chamber, 2-chamber, and long axis 2-dimensional ultrasound images of the heart will be acquired using a Philips EPIQ 7 ultrasound machine and stored for subsequent off-line analysis. Global longitudinal strain will be quantified using Philips QLAB advanced quantification software.

5.2.7. WSP Exposure Symptom Questionnaire

Please indicate if you are experiencing any of the symptoms or restrictions listed below, using the following scale to indicate the severity. Circle the number.

0 = NONE	(not present)
1 = TRACE/NOTICED	(barely detectable)
2 = MILD/LIGHT	(present, but not annoying)
3 = MODERATE	(present, but somewhat annoying)
4 = SEVERE/HEAVY	(present and very annoying and painful)

SYMPTOMS	NONE	TRACE	MILD	MODERATE	SEVERE
1. HEADACHE	0	1	2	3	4
2. IRRITATION OF THE NOSE	0	1	2	3	4
3. STUFFY NOSE/SINUS CONGESTION	0	1	2	3	4
4. RUNNY NOSE	0	1	2	3	4
5. DRY/SORE THROAT	0	1	2	3	4
6. PAIN on DEEP INSPIRATION	0	1	2	3	4
7. UNUSUAL FATIGUE OR TIREDNESS	0	1	2	3	4
8. EYE IRRITATION	0	1	2	3	4
9. SHORTNESS OF BREATH	0	1	2	3	4
10. SNEEZING	0	1	2	3	4
11. COUGH	0	1	2	3	4
12. WHEEZING/WHISTLING in CHEST	0	1	2	3	4
13. CHEST TIGHTNESS	0	1	2	3	4
14. SWEATING	0	1	2	3	4
15. Other _____	0	1	2	3	4

5.2.8. GI Symptom Questionnaire

Please indicate if you are experiencing any of the symptoms or restrictions listed below, using the following scale to indicate the severity. Circle the number.

0 = NONE	(not present)
1 = MILD	(minimally noticeable but would not cause you to stop normal activities such as going to work or school or physical exercise)
2 = MODERATE	(symptom level would not ordinarily cause you stop normal activities such as going to work or school although it might stop you from doing physical exercise)
3 = SEVERE	(symptom would cause you to consider not going to work or school or to seek medical attention such as calling a healthcare provider, going to student health, or going to the emergency room)

SYMPTOMS	NONE	MILD	MODERATE	SEVERE
1. INCREASE IN STOOLS	0	1	2	3
2. DIARRHEA	0	1	2	3
3. BLOATING/FULLNESS	0	1	2	3
4. STOMACH CRAMPING/PAIN	0	1	2	3
5. INCREASE IN PASSING GAS	0	1	2	3
6. VOMITING	0	1	2	3
7. NAUSEA	0	1	2	3
8. HEADACHE	0	1	2	3
9. EASY BRUISING OR BLEEDING	0	1	2	3
10. Other _____	0	1	2	3

6. Statistical Plan

6.1 Sample Size Determination

The primary endpoint of this study is Δ sputum %PMNs (post WSP – pre WSP [γ T]) at 4 hour vs (post WSP – pre WSP [placebo]) at 4 hours, and (post WSP – pre WSP [γ T]) at 24 hours vs (post WSP – pre WSP [placebo]) at 24 hours. Preliminary analyses from our screening study of the effects of 500 μ g/m³ WSP exposure on sputum neutrophilia in healthy volunteers and mild asthmatics demonstrated that, among “responders” (those participants with a $\geq 10\%$ increase in sputum neutrophils following WSP exposure), the mean increase in sputum %PMNs was $28.5 \pm 13\%$. In our studies of γ T vs placebo for mitigating LPS-induced change in sputum %PMNs in healthy volunteers (11) and mild asthmatics (26), we found a γ T treatment effect size of $14.5\% \pm 25.9$. Assuming $\beta=0.8$ and $\alpha=0.05$, a sample size of 28 healthy volunteers and mild asthmatics would be required to detect the same γ T treatment effect size. To account for a 25% attrition rate with human studies, we will inflate the sample size to 35 healthy volunteers and mild asthmatics. Importantly, we anticipate that we will decrease subject variability by only recruiting persons with $\geq 10\%$ increase in WSP-induced %PMNs in sputum during the screening protocol (the so-called “responders”).

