Subjects will be under direct supervision for 6 hours from the start of WSP challenge and will have contact information for after-hours access to a study physician. In the event of an unexpected event, such as wheezing or bronchospasm, the physician will follow the usual medical standard of care to treat the subject.

4. Subject Selection and Withdrawal

Preliminary results from our screening WSP exposure study have shown that approximately 57% of healthy volunteers were responsive to the inflammatory effects of WSP. Based on this experience, we estimate we will need to screen 50 volunteers to identify 28 who are responsive to inhaled WSP. Anticipating an attrition rate of 20%, we will need to identify 35 volunteers for the intervention study, requiring an overall screen of a minimum of 64 volunteers. There will be no gender or ethnic restrictions. The target completion goal is 28 healthy volunteers and mild asthmatics. Individuals who meet all of the following criteria are eligible for enrollment as study participants.

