4.3. Withdrawal or Termination

Participants will be terminated early from the study for the following reasons:

1. The participant elects to withdraw consent from all future study activities including follow up.
2. The participant is “lost to follow up” (i.e., no further follow up is possible because attempts to reestablish contact with the participant have failed).
3. The participant dies.
4. The participant develops a medical condition or is started on a new medication(s) not previously mentioned in the list of prohibited medications that, in the opinion of the investigator, may pose additional risks from participation in the study, may interfere with the participant’s ability to comply with study requirements or that may impact the quality of the data obtained from the study.
5. The participant meets any of the individual stopping rules as delineated.
6. The study is terminated for any reason.

Participants with early termination from this study will not be replaced.

5. Study Procedures

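### At the 25% attrition stated in Section 6.1, enrolling 35 leaves about 26 completers, not 28; Section 4 gives 20% for the same step

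*Combined protocol and SAP*

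**What the plan says.** Section 6.1 (Sample Size Determination) takes a treatment effect of 14.5 with a spread of 25.9 from the earlier endotoxin studies and concludes that "a sample size of 28 healthy volunteers and mild asthmatics would be required". The next sentence adds the attrition allowance: "To account for a 25% attrition rate with human studies, we will inflate the sample size to 35 healthy volunteers and mild asthmatics".

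The opening paragraph of Section 4 (Subject Selection and Withdrawal) makes the same step at another rate: "Anticipating an attrition rate of 20%, we will need to identify 35 volunteers for the intervention study". It then sets the goal: "The target completion goal is 28 healthy volunteers and mild asthmatics".

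The Study Summary also gives 35 subjects. Section 4.3 (Withdrawal or Termination) adds: "Participants with early termination from this study will not be replaced".

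**The concern.** Two attrition rates, 20% and 25%, are offered for one step from 28 to 35, and they cannot both be right. To keep *n* completers when a fraction *d* is lost, one enrols *n*/(1 − *d*). Section 6.1 appears to have used *n*(1 + *d*), which always falls short of what is needed.

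The attrition rate is what links enrolment to the number completing. If 25% is the real expectation, the trial as sized misses its own completion goal and its power falls just under the planned level. Because dropouts are not replaced, nothing later in the plan makes up the difference.

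**Working it through.** **Inputs**

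- Completers required: 28 (Sections 6.1 and 4).
- Enrolment: 35 (Study Summary, Sections 4 and 6.1).
- Attrition: 25% (Section 6.1), 20% (Section 4).
- Effect 14.5 and SD 25.9, in percentage points of sputum neutrophils (Section 6.1).
- Alpha 0.05 (Section 6.1).
- Power 0.80. Section 6.1 writes this as a beta of 0.8, which taken literally would be 20% power.
- Assumptions, because Section 6.1 is silent: the test is two-sided, and 25.9 is the SD of the within-subject difference between treatments.

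**Step 1. Reproduce the 28.** For a paired t-test the noncentrality is (14.5/25.9) × √n = 0.560 × √n, with n − 1 degrees of freedom.

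| Completers | Power |
|---|---|
| 26 | 0.7834 |
| 27 | 0.7996 |
| 28 | 0.8148 |

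The smallest n reaching 0.80 is 28, since 27 falls just short. The plan's base figure is therefore reproduced, which supports both assumptions and the reading of 0.8 as power.

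**Step 2. Reproduce the 35.**

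| Attrition *d* | 28/(1 − *d*) | 28 × (1 + *d*) |
|---|---|---|
| 20% | 28/0.80 = 35.0 | 28 × 1.20 = 33.6 |
| 25% | 28/0.75 = 37.3, so 38 | 28 × 1.25 = 35.0 |

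Section 4's 20% gives 35 by the correct formula. Section 6.1's 25% gives 35 only by the incorrect one.

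**Step 3. Completers from 35 enrolled.**

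- At 20%: 35 × 0.80 = 28.
- At 25%: 35 × 0.75 = 26.25, so about 26.

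**Step 4. Effect on power at 25%.** With 26 completers power is 0.783. That is 1.7 percentage points below the planned 0.80 and 3.1 points below the 0.815 available at 28.

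**Step 5. Chance of reaching the goal.** If each of 35 participants completes independently, the binomial probability of at least 28 completers is 0.32 when the completion probability is 0.75, and 0.60 when it is 0.80.

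**The case against.** The strongest reply is that this is a labelling slip. Since 35/28 = 1.25, the 25% is probably the inflation factor called an attrition rate by mistake. The numbers 28 and 35 agree wherever they appear, and Section 4 connects them correctly. On that reading 35 does cover the planned loss, and one figure in Section 6.1 is wrong. This is the likeliest explanation, and it means the shortfall depends on 25% being the true expectation. It does not remove the contradiction: the text presents 25% as an attrition rate, and nothing in the documents says which rate the sponsor expects.

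A second reply is that the consequence is slight. Against the planned 80% the loss is under two points. That is true, and the point should be given no more weight than that.

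A third is that Section 6.2 plans multiple imputation and a random effects model, so someone who leaves after period 1 may still contribute. This helps little. The paired comparison needs both periods. The model equations are headed for secondary and exploratory outcomes, although the text above them also mentions the model for the sputum response. Neither method creates completers, and neither reconciles 20% with 25%.

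**Conclusion.** The inconsistency is real. An enrolment of 35 matches 28 completers at 20% attrition and does not match them at 25%. At Section 6.1's own rate, about 26 would complete, and 38 would have to be enrolled to keep 28, three more than planned.

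The attrition arithmetic uses only figures printed in the documents. The power figures also rest on a two-sided test, on 25.9 being the SD of the paired difference, and on dropouts contributing nothing to the primary comparison. This is a modest error in planning figures that should be corrected. It does not threaten the design.

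**What to change.** Decide which loss is expected, then state one rate in both sections.

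- **If 20%:** change 25% to 20% in Section 6.1 and show 28/0.80 = 35. Section 4 stays as it is. The choice should reflect what the sponsor expects, and not only the fact that 20% makes the sum work.
- **If 25%, keeping 35:** in Section 6.1 state about 26 expected completers and about 78% power. Section 4 must then change too, both its 20% and its completion goal of 28.

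Both are changes of wording. The second makes one stated figure slightly less favourable. If the sponsor expects 25% and still wants 28 completers, enrolment has to be 38. At Section 4's responder rate of 57%, that means screening at least 38/0.57 = 66.7, so 67 volunteers against the stated minimum of 64. This is the only route with a real cost, and it is not needed to make the text consistent.

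At the same time, in the sentence before the attrition statement in Section 6.1, replace the beta of 0.8 with power 0.8 (beta 0.2). State there too that the test is two-sided and that 25.9 is the SD of the within-subject difference, if that is what was used.

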6.2. Statistical Methods

Our analytic plan was developed in collaboration with [name], the biostatistician for the CEMALB, who will oversee all statistical analysis. For analysis of sputum and circulating PMN responses as well as cytokine changes within each treatment group, we will use (i) descriptive analysis, (ii) two-sample comparison test, and (iii) random effects regression analysis (Equation 1) designed to take advantage of the crossover design (22). Specifically, we will use the tabular and graphic methods to describe/explore the basic relationship between the groups. We will then follow up by comparing the Δ sputum %PMNs (post WSP – pre WSP [γ T]) vs (post WSP – pre WSP [placebo]) using two-sample tests, either parametric (T-Test) or nonparametric (Wilcoxon signed-rank test), depending on whether the normality assumption is met. We will transform the data to achieve normality if needed. Finally, we will employ a random effect regression modeling technique (Equation 1) that allows us to assess treatment effect while accounting for potential period effect and carry-over effects. This approach is similar to those we have previously described to assess genotype effects (including the GSTM1 null genotype) on response to pollutants (11, 23-25) and is shown below. In all analyses, criterion for significance will be $p \leq 0.05$. To address potential missing data, we will employ multiple imputation methods to address this issue when appropriate; using techniques we have previously described (24).

Linear mixed model approach for global unified analysis of data for secondary and exploratory outcomes:

$$Y_{11k} = \mu + \pi_1 + \tau_1 + \beta X_k + s_{1k} + \epsilon_{11k}; Y_{12k} = \mu + \pi_2 + \tau_2 + \lambda_1 + \beta X_k + s_{1k} + \epsilon_{12k}$$

$$Y_{21k} = \mu + \pi_1 + \tau_2 + \beta X_k + s_{2k} + \epsilon_{21k}; Y_{22k} = \mu + \pi_2 + \tau_1 + \lambda_2 + \beta X_k + s_{2k} + \epsilon_{22k}$$

μ is the grand mean, π_1 and π_2 are period effects, τ_1 and τ_2 are treatment effects, λ_1 and λ_2 are carryover effects for different sequences, s_{1k} and s_{2k} are individual random effects within each sequence, and ϵ 's are random errors. Subscript k is for subjects.

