Study Center(s)	University of North Carolina Hospitals in Chapel Hill, North Carolina, 27599-7310
Objectives	To determine the efficacy of 1100 mg gamma tocopherol-enriched supplement for mitigating inhaled wood smoke particle-induced airway inflammation in healthy adults with no more than mild asthma
Number of Subjects	35 subjects

Diagnosis and Main Inclusion Criteria	Healthy adult volunteers with no more than mild asthma
Study Product, Dose, Route, Regimen	Gamma E Gems (J.R. Carlson Laboratories, Inc., [name] Arlington Heights, IL 60004.)
Statistical Methodology	Change in sputum % neutrophils (%PMNs) [Δ postWSP-preWSP (γ T) vs Δ postWSP-preWSP (placebo)]. Statistically significant differences will be determined using two-sample tests, either parametric (t-test) or non-parametric (Wilcoxon signed-rank test) depending on whether the normality assumption is met.

1. Introduction

This document is a protocol of a human research study. This study is to be conducted according to US and international standards for Good Clinical Practice (FDA Title 21 part 312 and International Conference on Harmonization guidelines), applicable government regulations and Institutional research policies and procedures.

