6.4. Randomization plan

The randomization schedule will be generated by [name] (biostatistician) and provided to the investigational pharmacy. Only [name] and the pharmacist will have access to the randomization schedule. Subjects will be allocated to begin the first period of the crossover study with placebo or γ T treatment using permuted block randomization with a block size of 4 (2 placebo, 2 γ T for the first treatment period of the protocol).

7. Monitoring and Risk Minimization

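### The Study Summary lets a test with no period term decide the primary %PMN contrast, and section 6.2 does not say whether its period-adjusted model takes precedence

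*Combined protocol and SAP*

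**What the plan says.** Section 6.4 randomises participants to start with placebo or gamma tocopherol by "permuted block randomization with a block size of 4", so what is randomised is the treatment order. For the change in sputum %PMN, the Study Summary states: "Statistically significant differences will be determined using two-sample tests, either parametric (t-test) or non-parametric (Wilcoxon signed-rank test". Section 6.2 repeats this for the same contrast: "using two-sample tests, either parametric (T-Test) or nonparametric (Wilcoxon signed-rank test), depending on whether the normality assumption is met".

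Section 6.2 also contains a period-adjusted analysis. Its opening sentence on methods names three approaches for sputum PMN responses, the third being random effects regression. It later says that this model allows for possible period and carryover effects. The equation itself, however, is introduced as "Linear mixed model approach for global unified analysis of data for secondary and exploratory outcomes". No sentence ranks the model against the tests for the primary endpoint.

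On dropout, section 4.3 states: "Participants with early termination from this study will not be replaced". Expected attrition is 20% in section 4 and 25% in section 6.1.

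**The concern.** The t-test and the signed-rank test on within-person treatment differences treat every participant alike, whichever treatment came first. A shift between periods enters those differences with one sign in one sequence and the opposite sign in the other. With equal sequences the shift cancels from the mean but is counted as random variation, so the standard error is too large. With unequal sequences part of it stays in the treatment estimate.

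A shift is plausible, though the documents do not quantify it. The Period 2 exposure is at least the third smoke challenge, after screening and Period 1. It follows more sputum inductions and comes at least four weeks later. The change score may not absorb a shift: the visit lists show an in-study pre-exposure sputum only at Visit 0 (section 5.1.2), and at Visits 2 and 5 only a 4-hour post-exposure sample (section 5.1.4). If one baseline serves both periods, it cancels from the treatment contrast and leaves the shift in place.

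At stake are the precision and, if completers are unequal, the value of the primary estimate. Which of two listed analyses would prevail if they disagreed is also open.

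**Working it through.** **Inputs.** Section 6.1 gives a treatment effect of 14.5 points, SD 25.9, alpha 0.05, power 0.80 (written as beta), 28 evaluable and 35 enrolled. The tests are taken as two-sided, and 25.9 as the SD of the paired difference net of period. Both are assumptions. The period shift is not given and is assumed to be 0 to 15 points.

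**The plan's own figure.** For a paired t-test with n = 28, SE = 25.9/√28 = 4.89 and power by the noncentral t is 81.5%. At n = 27 it is 79.96%, so 28 is the smallest n reaching 80%. The plan's N is reproduced, which also supports reading the two-sample tests as paired.

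**Mechanism.** Let D be the Period 2 minus Period 1 shift and τ the benefit (placebo minus gamma tocopherol). The within-person benefit has mean τ + D in the gamma-tocopherol-first sequence (n1 completers) and τ − D in the placebo-first sequence (n2 completers). With n = n1 + n2:

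- Unadjusted bias = D × (n1 − n2)/n. At 15/11 and 10 points: 10 × 4/26 = 1.5.
- Unadjusted SE when balanced ≈ √[(25.9² + D² × n/(n − 1))/n]. At 14/14 and 10 points: √[(670.8 + 103.7)/28] = 5.26, about 7% above 4.89.
- Adjusted: take Period 1 minus Period 2 in each person, with means −τ − D and τ − D in the two sequences. Half the difference between them is τ, free of D. SE = ½ × 25.9 × √(1/n1 + 1/n2), which is 4.89 at 14/14 and 5.14 at 15/11, on n − 2 degrees of freedom.

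**Results.** Adjusted power is exact. Unadjusted figures come from simulation, 200,000 trials per setting. Where two powers appear, the first is for bias favouring the drug and the second for bias against it.

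| Completers | Shift | Bias | Power, unadjusted | Power, adjusted | Type I error, unadjusted |
|---|---|---|---|---|---|
| 14/14 | 0 | 0 | 81.5% | 81.4% | 5.0% |
| 14/14 | 5 | 0 | 80% | 81.4% | 4.6% |
| 14/14 | 10 | 0 | 77% | 81.4% | 3.6% |
| 14/14 | 15 | 0 | 72% | 81.4% | 2.4% |
| 15/11 | 0 | 0 | 78.3% | 77.2% | 5.0% |
| 15/11 | 5 | ±0.8 | 81% or 73% | 77.2% | 4.9% |
| 15/11 | 10 | ±1.5 | 82% or 64% | 77.2% | 4.4% |
| 15/11 | 15 | ±2.3 | 82% or 52% | 77.2% | 3.8% |

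**How unequal the sequences will be.** In blocks of 4, 35 participants split 18/17. With independent random dropout of 20% or 25%, the mean absolute difference in completers is about 2. A difference of 4 or more occurs in 16% or 19% of trials. A difference of 2 among 28 gives a bias of 10 × 2/28 = 0.7 points at a 10-point shift.

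**Averaged over dropout** (18/17 randomised, 20% random loss), unadjusted power at a 10-point shift is 78% or 75%, depending on direction, against 81% adjusted. At 5 points it is 81% or 79%, against 81%.

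**The case against.** The strongest reply is that period adjustment is already in the plan: section 6.2 lists the random effects model for sputum PMN responses. A reader might infer from the tests alone that the primary endpoint has no period-adjusted analysis at all. The documents do not support that. What stands is narrower. The Study Summary names only the unadjusted tests as deciding significance, the equation's heading leaves out the primary endpoint, and nothing settles which result governs.

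A second reply is that the effect may be small. No shift size is documented, and 10 and 15 points are 69% and 103% of the 14.5-point treatment effect. At 5 points and 14/14 the loss is about 1 point of power. If dropout is unrelated to sequence, the bias averages near zero over repeated trials. All of this stands, although the one trial that is run keeps whatever imbalance it ends with.

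Third, section 6.1 does not say whether 25.9 is net of period. If it came from raw paired differences that already contained a similar shift, N = 28 already allows for some of the lost power. That would not remove the bias under unequal sequences.

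Fourth, section 6.2 allows multiple imputation where suitable, which could reduce completer-only imbalance. The plan does not say whether it applies to the primary test or whether period and sequence would enter the imputation model.

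**Conclusion.** The point holds as an unresolved choice of primary analysis in which the written rule favours the weaker method. Followed literally, the Study Summary lets a test with no period term decide the primary contrast. With balanced sequences and a 5 to 15 point shift, this costs about 1 to 10 points of power and makes the test conservative. At 15/11 it moves the estimate by 0.8 to 2.3 points in a direction that cannot be known in advance.

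Two stronger readings should be resisted. One is that the primary p-value is wrong whenever the periods differ: at 14/14 and 5 points, type I error is 4.6% and power about 80%, so the departure is slight. The other is that unequal sequences inflate false positives: at 15/11, type I error stays at or below 5% throughout. It exceeds 5% only at more extreme splits such as 18/10, where it is about 6.7% at a 10-point shift. If exactly 28 of an 18/17 start complete at random, that split has a probability of about 0.3%.

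The sizes rest on the assumed range of shifts, an additive shift common to all participants, an SD of 25.9 net of period, and analysis of completers. The case for changing the plan rests mainly on the remedy being nearly free while planned power, at 81.5%, leaves little reserve.

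**What to change.** In the Study Summary and section 6.2, name one primary analysis for %PMN at each time point, the period-adjusted crossover contrast. Compute each participant's Period 1 minus Period 2 difference and compare it between the two randomised sequences with a two-sample t-test. Report half the difference in sequence means as the treatment effect, with its confidence interval. Use the rank-sum test on the same differences as the nonparametric fallback, in place of the signed-rank test. Leave carryover terms out of this primary analysis.

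State in section 6.2 that Equation 1 is supportive for %PMN, and amend its heading to match, so that the heading and the section's opening sentence no longer conflict.

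The cost is wording and one degree of freedom, with no new data or participants. If there is no period effect, power falls from 81.5% to 81.4% at 14/14, by about 1 point at 15/11 (78.3% to 77.2%), and by about 3.5 points at 18/10 (81.5% to 78.0%).
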